2 HYPOTHESIS

Primary: Non-ablative SBRT (800 cGy X 3 fractions) given 5-7 days preoperatively in selected patients with stage I-II NSCLC will result in alterations in the tumor immunoprofile, tumor microenvironment, gene expression profiles and peripheral blood immune repertoire.

Secondary: This regimen will be well tolerated, associated with minimal toxicity, and will not impact on wound healing.

It should be noted that this is designed as a pilot trial, so statistical analysis will be descriptive and formal hypothesis-testing will not be performed

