3.2 Secondary Objectives

- Assess the impact of non-ablative SBRT (800 cGy X 3 fractions) prior to surgical resection on peri- and post-operative complication rate, and wound healing.
 - Surgical complications will be assessed using the Clavien-Dindo Classification system. The Clavien-Dindo classification system has been validated and established as an “objective, reproducible” grading classification.¹⁷
 - This classification system uses a grading based on the extent of intervention needed to manage a specific complication. See appendices C and D for examples.
 - Wound healing will be assessed and charted by the study cardio-vascular (CV) surgeons using the General Thoracic Surgery Database with particular references to pages 246-248. See Appendix E.
- Describe loco-regional control, metastasis-free survival, disease-free and overall survival in patients treated on this trial with pre-operative SBRT followed by surgery

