3.4 Secondary Endpoints

What is being measured	Measurement time frame	Measurement Tool

The impact of pre-surgical non-ablative SBRT on peri- and post-operative surgical complication rate
	
From Day of post-SBRT surgery through 6 month (± 2 months) post-operative follow up visit
	
Medical Record Review Clavien-Dindo Classification system

The impact of pre-surgical non-ablative SBRT on wound healing
	
From Day of post-SBRT surgery through 6 month (± 2 months) post-operative follow up visit
	
Medical record review General Thoracic Surgery Database.

Loco-regional control, metastasis-free survival, disease free and overall survival
	
From Day of enrollment through 36 month follow up visit
	
Medical record review

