4.3 End of Study Definition

End of study is defined as the time of completion of 36 month follow-up after enrollment of all patients still eligible for follow-up (excluding death and drop-out prior to 36 months).

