6.2 Participant Replacement

Participants will not be replaced once they have successfully completed surgery.

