- Computed tomography will be the primary image platform for targeting and treatment planning. The target lesion will be outlined by the treating physician and will be designated as the gross tumor volume (GTV), which will also be designated the clinical target volume (CTV)(i.e. GTV=CTV). 4DCT data sets will be used to generate internal tumor volume (ITV). The PTV will include the ITV plus an additional 0.5 cm margin uniformly applied to the ITV. Per physician discretion, these volumes can be adjusted based on each patient's clinical situation and anatomy.

Dosimetry

- Three-dimensional coplanar or non-coplanar beam arrangements will be custom designed for each case to deliver highly conformal prescription dose distributions. Non-opposing, noncoplanar beams are preferable. For purposes of dose planning and calculation of monitor units for actual treatment, this protocol will require tissue density heterogeneity corrections.

Prescription Dose Constraints for Treatment Planning

The prescription isodose surface will be chosen such that 95% of the target volume (PTV) is conformally covered by the prescription isodose. Dose homogeneity within the GTV of +/- 5% is highly recommended.

Organs At Risk (OAR) visible in the planning CT will be contoured. Dose constraints are defined below.

Dose Constraints

- Modification as defined in the chart below** of the Dose Constraints as defined by RTOG 9501 Arm 2 12 Gy X 4 is the basis of dose limitations of the organs at risk to be used this protocol.²¹
- The risk of end-organ damage as defined in the table is anticipated to be less than 1%.**

Organ at Risk	Volume	Volume Max (Gy)	Max Point Dose (Gy)	Endpoint (\geq Grade 3)
Spinal Cord	<0.35 cc <1.2 cc	10.4 Gy (5.2 Gy/fx) 6.8 Gy (3.4 Gy/fx)	13 Gy (6.5 Gy/fx)	Myelitis
Esophagus	<5 cc	9.4 Gy (4.7 Gy/fx)	15 Gy (7.5/fx)	Stenosis/fistula
Brachial Plexus	<3 cc	11.8 Gy (5.9 Gy/fx)	13.6 Gy(6.8Gy/fx)	Neuropathy
Heart/Pericardium	<15 cc	14 Gy (7 Gy/fx)	17 Gy (8.5 Gy/fx)	Pericarditis
Great vessels	<10 cc	21.5 Gy (10.75 Gy/fx)	24.5 Gy (12.25 Gy/fx)	Aneurysm
Trachea and Large Bronchus	<4 cc	7.8 Gy (3.9 Gy/fx)	17.4 Gy (8.7 Gy/fx)	Stenosis/fistula
Rib	<1 cc	16 Gy (8 Gy/fx)	20 Gy (10Gy/fx)	Pain or fracture
Skin	<10 cc	16.6 Gy (8.3 Gy/fx)	18 Gy (9 Gy)	Ulceration
Stomach	<10 cc	8.8 Gy (4.4 Gy/fx)	18.6 Gy (6.8 Gy)	Ulceration/fistula
Parallel Tissue	Critical Volume (cc)	Critical Volume Dose Max (Gy)		Endpoint (\geq Grade 3)

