Lung (Right & Left)	1500 cc	5.8 Gy (2.9 Gy/fx)		Basic Lung Function
Lung (Right & Left)	1000 cc	6.2 Gy (3.1 Gy/fx)		Pneumonitis

Quality assurance

Patient safety will be ensured with effective treatment delivery with a robust quality assurance protocol as defined below.

- Prior to treatment each patient will be discussed by quality assurance team as defined by a study investigator, treating radiation oncologist, study physicist and dosimetrist.
- The treating radiation oncologist will confirm prior to the first fraction delivery that the radiation treatment plans must meet target dose levels for dose homogeneity..
- Prior to plan approval, the organ at risk dose volume histogram must be verified by the treating radiation oncologist and physicist. Dose constraints as defined shall not be exceeded.

- Image-guided radiation treatment (I GRT/SBRT) with cone beam CT will be used to verify patient positioning prior to each treatment. And will require approval by the treating radiation oncologist prior to treatment delivery.

Possible side effects of SBRT as listed below.

The likelihood of the defined organ risk/toxicity is anticipated to be less than 1%, as the dose constraints defined in this protocol are well below the RTOG-0915 defined dose constraints for SBRT of the lung.

Organ at Risk	Possible Side Effect	Volume	Volume Max (Gy) Dose threshold as defined for end organ damage in RTOG 0915
Spinal Cord	Myelitis	< 0.35 cc < 1.2 cc	20.8 Gy (5.2 Gy/fx) 13.6 Gy (3.4 Gy/fx)
Esophagus	Stenosis/fistula	< 5 cc	18.8 Gy (4.7 Gy/fx)
Brachial Plexus	Neuropathy	< 3 cc	23.6 Gy (5.9 Gy/fx)
Heart/Pericardium	Pericarditis	< 15 cc	28 Gy (7 Gy/fx)
Great vessels	Aneurysm	< 10 cc	43 Gy (10.75 Gy/fx)
Trachea and Large Bronchus	Stenosis/fistula	< 4 cc	15.6 Gy (3.9 Gy/fx)
Rib	Pain or fracture	< 1 cc	32 Gy (8 Gy/fx)
Skin	Ulceration	< 10 cc	33.2 Gy (8.3 Gy/fx)
Stomach	Ulceration/fistula	< 10 cc	17.6 Gy (4.4 Gy/fx)
Parallel Tissue	Possible Side Effect	Critical Volume (cc)	Critical Volume Dose Max (Gy)
Lung (Right & Left)	Basic Lung Function	1500 cc	11.6 Gy (2.9 Gy/fx)
Lung (Right & Left)	Pneumonitis	1000 cc	12.4 Gy (3.1 Gy/fx)

Surgery

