11.1 Adverse Event Monitoring

Baseline adverse events are recorded and graded using NCI Common Terminology Criteria for Adverse Events (CTCAE) version 5.0⁴¹. Additional serious adverse event and adverse event monitoring begins after initiation of study intervention and ends 36 months following surgery (i.e.; end of study).

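### The hypothesis covers tolerability and toxicity of the SBRT regimen, but both named safety endpoints start at surgery and end at about month 6, so part of the toxicity and any irradiated but unoperated participant belong to no safety endpoint

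*Protocol*

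**What the plan says.** The secondary hypothesis in section 2 has three parts: "This regimen will be well tolerated, associated with minimal toxicity, and will not impact on wound healing". The same section says that analysis will be descriptive, without formal testing.

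Section 3.2 turns the safety part into an objective on the effect of SBRT "prior to surgical resection on peri- and post-operative complication rate, and wound healing". Section 3.4 names two matching endpoints, Clavien-Dindo surgical complications and wound healing by the General Thoracic Surgery Database, each measured "From Day of post-SBRT surgery through 6 month (± 2 months) post-operative follow up visit". The third secondary endpoint (loco-regional control, metastasis-free, disease-free and overall survival) runs from enrollment to month 36 but does not measure toxicity. Section 12.1 plans summaries of surgical complications, wound healing and tumor control.

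On replacement, section 6.2 says only: "Participants will not be replaced once they have successfully completed surgery".

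Adverse events are assessed at simulation and at each fraction (9.1.1), collected from the start of the intervention (11.1, 11.2), followed after removal from therapy (9.5) and reviewed by the DSMC (14, 14.3). Section 11.1 says that monitoring "ends 36 months following surgery (i.e.; end of study"), whereas section 4.3 says: "End of study is defined as the time of completion of 36 month follow-up after enrollment".

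**The concern.** SBRT is the experimental component, and the hypothesis makes a claim about how the regimen is tolerated. The endpoints meant to address that claim begin only when the participant is operated on. They therefore select on reaching surgery, which is itself an outcome that toxicity could affect. If an irradiated participant had a severe event, missed surgery and was replaced, the named endpoints could show a clean record in 10 operated participants while the most informative case sat outside them.

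The period over which a toxicity summary would run is also stated in conflicting ways. This matters most for participants who go on to adjuvant systemic therapy, which section 8.1 (Surgery) allows, and for those who are never operated on.

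**Working it through.** The Protocol gives no alpha, power or target rate for tolerability, so there is no figure of its own to reproduce. The check sets the time windows and denominators side by side.

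**1. Time covered by the two safety endpoints.** Inputs: fraction 1 on day 1, fraction 3 on day 3, surgery on days 8-10 (9.1.1 and the schedule in 9.3); endpoint window from surgery to month 6 ± 2 (3.4); adverse event monitoring to 36 months after surgery (11.1, 11.2).
- Before surgery: 8 − 1 = 7 days to 10 − 1 = 9 days after first irradiation lie outside both endpoints. The interval lengthens if the fractions are not given on consecutive days, which 8.1 permits.
- After surgery: the window closes between month 6 − 2 = 4 and month 6 + 2 = 8. Of 36 months of monitoring, 36 − 8 = 28 to 36 − 4 = 32 months lie outside both endpoints.

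**2. Participants covered.** Both endpoints need an operation. Section 6.2 bars replacement only after completed surgery, so by implication an irradiated participant who is not operated on may be replaced. With 10 operated participants and r replaced after irradiation, coverage is 10/(10 + r). The Protocol gives no rate of missed surgery, so r is an assumption:

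| r | Operated / irradiated | Coverage |
|---|---|---|
| 0 | 10/10 | 100% |
| 1 | 10/11 | 90.9% |
| 2 | 10/12 | 83.3% |

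**3. What this could do to a reported rate (illustration).** Suppose every replaced participant had a grade 3 or higher event before surgery and nobody else had one. Exact (Clopper-Pearson) 95% limits for x events in n are the 2.5% quantile of Beta(x, n − x + 1) and the 97.5% quantile of Beta(x + 1, n − x); for x = 0 the limits are 0 and 1 − 0.025^(1/n).
- Operated only: 0/10, with upper limit 1 − 0.025^(1/10) = 30.8%.
- All irradiated, r = 1: 1/11 = 9.1%, 95% CI 0.2% to 41.3%.
- All irradiated, r = 2: 2/12 = 16.7%, 95% CI 2.1% to 48.4%.

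The intervals overlap widely. What changes is whether the events appear in the tolerability result at all.

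**4. End of adverse event monitoring and of follow-up.**

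| Place | End point |
|---|---|
| 11.1 | 36 months after surgery, equated with end of study |
| 11.2 | 36 months after surgery |
| Appendix B, Adverse Event Monitoring | 36 months after surgery, or start of a new anti-cancer therapy if earlier |
| 4.3 | End of study: 36-month follow-up counted from enrollment |
| 9.1.2 | Last follow-up at month 36 after enrollment |

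Under Appendix B, collection could stop when adjuvant systemic therapy begins; under 11.1 and 11.2 it would continue. A period that ends relative to surgery is undefined for a participant who has none.

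**The case against.** The strongest reply is that this is a descriptive pilot of 10, that its objectives and endpoints agree with each other, and that the mismatch is with one sentence of the hypothesis. All adverse events are collected, and the DSMC follows every treated participant. Adverse event tables and analysis sets are often left to the SAP, which is not shown. Clavien-Dindo counts any deviation from the normal postoperative course (Appendix C), so some SBRT toxicity after surgery would be graded there. Overall survival runs from enrollment, so a death before surgery falls in a named endpoint.

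Much of this stands, and it narrows the point to non-fatal toxicity before surgery, toxicity after about month 6, and participants not operated on. It does not remove the point. Objectives and endpoints are fixed in this document, and those it names cannot answer its own hypothesis for everyone treated. DSMC review is monitoring, not a reported endpoint.

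A reader might infer three stronger claims, none of which the document supports:
- **That early toxicity goes unrecorded.** It is recorded from the first fraction.
- **That replaced participants are dropped from analysis.** Section 6.2 does not say so. Section 6.1 excludes screen failures explicitly, no such wording applies to treated participants, and 9.5 continues their safety follow-up. The Protocol is simply silent on whether they stay in a safety denominator.
- **That the endpoints are at fault for not checking the organ toxicity figure.** Section 8.1 says "The likelihood of the defined organ risk/toxicity is anticipated to be less than 1"%. That is a planning expectation, justified by the dose constraints, and not an objective or threshold. Ten participants could not verify it under any endpoint, since even 0/10 leaves an upper limit of 30.8%.

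**Conclusion.** The point holds in its narrow form. The hypothesis on tolerability and toxicity is wider than the safety endpoints in 3.4 and the summaries in 12.1. On the planned schedule, the 7 to 9 days after first irradiation and the last 28 to 32 of 36 months after surgery lie outside both safety endpoints, as does any irradiated participant without surgery. How many participants that last group would contain is unknown; coverage of 10 of 11 or 10 of 12 rests on assumed counts, and permission to replace is inferred from what 6.2 bars.

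The conflict over when adverse event monitoring ends is a separate inconsistency. It needs no assumption and affects which events are captured.

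Both should be corrected. Neither undermines the primary immunological objective, and neither means that safety data are being lost before surgery.

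**What to change.** 1. In 3.4, keep the two surgical endpoints and label them as conditional on surgery.
2. Add to 3.4 and 12.1 (with a matching line in 3.2) a descriptive tolerability summary in all participants who receive at least one SBRT fraction, including any later replaced: CTCAE v5.0 events by grade from fraction 1, with the proportion at grade 3 or higher; and the proportion not reaching surgery, or not within the planned window, with reasons. Report each proportion as x/N with an exact 95% CI.
3. State in 6.2 that a participant replaced after irradiation stays in this set.
4. Separately, reconcile the end of adverse event monitoring and follow-up across 4.3, 9.1.2, 11.1, 11.2 and Appendix B, and define the period for participants who are not operated on.

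The cost is protocol wording and one extra table from adverse event and off-treatment data already collected. The intervals will be wide, and reported tolerability may look slightly less favourable than in operated participants alone.

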3 OBJECTIVES AND ENDPOINTS

3.1 Primary Objective

Assess the impact of non-ablative SBRT (800 cGy X 3 fractions) on immunomodulation in NSCLC tumor cells through analysis of targeted cell surface, tumor immune microenvironment, gene expression profile, radiation mediated changes in T-cell repertoire in tumor tissue and peripheral blood and circulating tumor cell surface expression.

3.2 Secondary Objectives

- Assess the impact of non-ablative SBRT (800 cGy X 3 fractions) prior to surgical resection on peri- and post-operative complication rate, and wound healing.
 - Surgical complications will be assessed using the Clavien-Dindo Classification system. The Clavien-Dindo classification system has been validated and established as an “objective, reproducible” grading classification.¹⁷
 - This classification system uses a grading based on the extent of intervention needed to manage a specific complication. See appendices C and D for examples.
 - Wound healing will be assessed and charted by the study cardio-vascular (CV) surgeons using the General Thoracic Surgery Database with particular references to pages 246-248. See Appendix E.
- Describe loco-regional control, metastasis-free survival, disease-free and overall survival in patients treated on this trial with pre-operative SBRT followed by surgery

3.3 Primary Endpoints

What is being measured	Measurement time frame	Measurement Tool

The impact of non-ablative SBRT on Immunomodulation in tumor cells
 
Pre and post study intervention biopsy tissue comparison of immunomodulatory parameters including but not limited to PDL1, PDL2, HCA2, IDO, HC10, B2m, Calreticulin, MHC-1, Fas, ICAM
	
From time of consent and collection of archival tumor tissue to time of surgery with collection of post-study intervention tumor tissue.
	
Techniques anticipated include but are not limited to: Immunohistochemistry, Targeted Nanostring (PanCancer ImmunoOncology 360; PanCancer Progression Panel), CTC Isolation, Tumor tissue and peripheral blood T-cell repertoire

3.4 Secondary Endpoints

What is being measured	Measurement time frame	Measurement Tool

The impact of pre-surgical non-ablative SBRT on peri- and post-operative surgical complication rate
	
From Day of post-SBRT surgery through 6 month (± 2 months) post-operative follow up visit
	
Medical Record Review Clavien-Dindo Classification system

The impact of pre-surgical non-ablative SBRT on wound healing
	
From Day of post-SBRT surgery through 6 month (± 2 months) post-operative follow up visit
	
Medical record review General Thoracic Surgery Database.

Loco-regional control, metastasis-free survival, disease free and overall survival
	
From Day of enrollment through 36 month follow up visit
	
Medical record review

4 STUDY DESIGN

4.1 Overall Design

This is a single arm pilot study. Participants with medically operable NSCLC will receive SBRT 800 cGy X 3 fractions delivered 5-7 days prior to planned surgery.

4.2 Justification for Dose

Published literature shows that cytotoxic doses of XRT (e.g. 1800-2000 cGy x3) may not elicit a clinically meaningful alteration in the immune profile. In addition, studies using an animal model have concluded a fractionated regimen induces a greater abscopal effect than single dose radiation. Furthermore, these studies showed a regimen of 800 cGy X 3 fractions yielded the most significant changes in the immune profile compared to 2000 cGy X 1 or 600 cGy X 5.¹⁸

Based on these prior data, we chose 800 cGy x 3 for this trial.

4.3 End of Study Definition

End of study is defined as the time of completion of 36 month follow-up after enrollment of all patients still eligible for follow-up (excluding death and drop-out prior to 36 months).

5 PARTICIPANT SELECTION

Patients with Stage 1-2 Non-Small Stage Lung Cancer and who are candidates for oncological surgical resection may be eligible for this trial if they meet all entry criteria.

5.1 Inclusion Criteria

PARTICIPANT MRN		PARTICIPANT INITIALS
Verified	Criteria	
	5.1.1	Ability of participant OR Legally Authorized Representative (LAR) to understand this study, and participant or LAR willingness to sign a written informed consent
	5.1.2	Males and females age ≥ 18 years
	5.1.3	ECOG Performance Status 0 - 1 (Appendix A.)
	5.1.4	Women of childbearing potential must have a negative serum pregnancy test 48 hours prior to initiating study intervention.
	5.1.5	Histological confirmation of Stage I or II NSCLC
	5.1.6	Candidate for oncologic surgery (lobectomy or sub lobar resection)

PARTICIPANT MRN		PARTICIPANT INITIALS		
Verified	Criteria			
	5.1.7	Adequate diagnostic biopsy tissue to allow for pre-SBRT tumor analysis		
	5.1.7	Lesion must be located peripherally, ≥ 2 cm from bronchial margin and 1 cm from visceral pleura with location deemed acceptable by cardiothoracic surgeon for resection.		
	5.1.8	Pulmonary function: Baseline PFTs including adequate FEV1 deemed by cardiothoracic surgeon to be acceptable for oncologic surgery, with a predicted post-operative FEV1 of 40% or greater and DLCO of 40% or greater.		
Adequate organ function, defined as follows:		Result	Date	
		White blood cell (WBC) count $\geq 3.0 \times 10^3$ cells/mm ³		
		Hemoglobin ≥ 10 g/dL		
		Absolute Neutrophil Count ≥ 1.5 K/UL		
		Platelets ≥ 150 K/UL		
		Serum creatinine clearance > 50 mL/min		
		Total bilirubin $\leq 2.0 \times$ ULN		
		Aspartate aminotransferase and alanine aminotransferase $\leq 2.5 \times$ ULN		
		Women of child-bearing potential and men with partners of child-bearing potential must agree to practice sexual abstinence or to use the forms of contraception listed in Child-Bearing Potential/Pregnancy section for the duration of study participation and for 6 months following completion of therapy.		

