6 CHILD-BEARING POTENTIAL / PREGNANCY

Because the effect of the study intervention is considered possibly teratogenic and has potential risks to the fetus, pregnant females will not be included in the study. However, no female of childbearing potential will be excluded from the study.

An effective form of contraception of the woman's choice will be required during study participation. Participants should not get pregnant, breastfeed, donate sperm or father a child while participating in this study and for **6 months** after the last dose of the study medication.

Women of childbearing potential and male participants must agree to use adequate contraception (hormonal or barrier method of birth control; abstinence) prior to study entry and for the duration of study participation. If a woman becomes pregnant or suspects she is pregnant while participating in this study or if her male partner is a participant in this study, the treating physician should be informed immediately.

Child-bearing potential is defined as any female (regardless of sexual orientation, having undergone a tubal ligation, or remaining celibate by choice) who meets the following criteria:

- Has either not undergone a hysterectomy or bilateral oophorectomy or has not been naturally postmenopausal for at least 12 consecutive months.

Participants must agree to use one of the following acceptable forms of birth control.

- Sexual Abstinence
- One barrier method (cervical cap with spermicide plus male condom; diaphragm with spermicide plus male condom) PLUS hormonal method (oral contraceptives, implants, or injections) or an intrauterine device (e.g., Copper-T).

If a woman becomes pregnant or suspects she is pregnant while participating in this study, she should inform her treating physician immediately.

If the partner of a man becomes pregnant or suspects she is pregnant while he is participating in this study, he should inform his treating physician immediately.

Men of child-bearing potential must not father a child or donate sperm while receiving investigational product and for **6 months** after their last study intervention.

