7.2 Registration Process

The University of Kansas Cancer Center participant registration is accessible for registration Monday through Friday, 8:00 AM to 5:00 PM Central Time. Please allow up to 24 hours for completion of registration.

The registration procedures are as follows:

1. Obtain written informed consent prior to the performance of any study related procedures or assessments. Tests required at screening and performed as part of customary care prior to signing consent, are allowed IF those tests were performed within the timeframe listed in Participant Selection section.
2. Complete appropriate baseline demographic information in CRIS. Print, complete and obtain appropriate signatures for the inclusion/exclusion criteria to document eligibility. Maintain completed documents in participant's research record. Participants must meet all eligibility criteria to be eligible for registration.
3. Use the hyperlink at the bottom of the eligibility criteria or in the CRIS system, complete information and submit to initiate the registration process.
4. Email confirmation of registration will be sent to the person initiating the registration. Registration confirmation should be maintained as part of the participant's research record.

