9 STUDY PROCEDURES AND SCHEDULE

9.1 Screening/Enrollment/Baseline

SCREENING VISIT

- Informed Consent
- Cancer history
- Demographics - including date of birth, gender, race, and zip code
- Review participant eligibility criteria to ensure participant qualification for study entry
- Physical exam to include vital signs, weight and height at baseline – which helps in the evaluation for surgical candidacy
- Baseline medical history to aid in assessment of possible adverse events
- ECOG Performance Status
- Pulmonary function test
- CBC with differential (± 3 Days)
- CMP (Serum chemistries) (± 3 Days) Serum chemistries to include: albumin, alkaline phosphatase, ALT/SGPT, AST/SGOT, BUN, creatinine, electrolytes (sodium, potassium, calcium, chloride, bicarbonate), glucose, total bilirubin, magnesium, lactate dehydrogenase (LDH), phosphate
- Urinalysis(± 3 Days)

- Urine pregnancy test (women only) (\pm 7 Days)
- Imaging (Chest) – CT preferred.
 - IV and oral contrast will be used for all imaging unless contraindicated. In the event the participant is intolerant to the contrast agent, an alternative imaging modality may be used. If CT contraindicated – MRI will be allowed (IV contrast will be used unless contraindicated). The same type of imaging used at screening must continue to be used throughout the study. Studies will be evaluated using RECIST Version 1.1.²²
- **Required collection of archival tumor biopsy tissue (either from initial diagnosis of lung cancer done prior to any study intervention or from any subsequent biopsy), for translational studies.**

A formalin-fixed paraffin-embedded (FFPE) tumor specimen in a paraffin block (preferred) or at least 15 slides containing unstained, freshly cut, serial sections should be submitted along with an associated pathology report prior to study enrollment. If only 10 to 14 slides are available, the specimen may still be used, after Principal Investigator confirmation has been obtained.
- **Required fresh tumor biopsy for translational studies.**

If archival tumor tissue is unavailable or is determined to be unsuitable for required testing, if participant consents, then fresh tumor tissue can be obtained from a biopsy performed after screening.

If participant does not consent, they cannot participate in this study.

Refer to Lab Manual for additional information on tumor specimens collected at screening.

At any time after enrollment and before surgery

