9.1.1 Procedures During Study Intervention

Day 0 - Simulation

- Radiation Simulation
- Adverse event assessment

Day 1 – Prior to 1st fraction

- Blood collection for translational studies

Day 1 – 1st Fraction

- Radiation – Fraction 1
- Adverse event assessment

Day 2 – 2nd Fraction

- Radiation – Fraction 2
- Adverse event assessment

Day 3 – 3rd Fraction

- Radiation – Fraction 3
- Adverse event assessment

NOTE: There is a 5-7 day rest period after radiation and before surgery.

Day of Surgery (Occurs during days 8-10)

- ECOG
- CBC with Differential (± 3 Days)
- CMP (Serum Chemistries) (± 3 Days)
- Physical exam
- Adverse event assessment
- Peri-operative surgical complication assessment
- Blood collection for translational studies BEFORE surgery
- Surgical specimen collection

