9.3 SCHEDULE OF EVENTS TABLE

Screening Period	Screening & Baseline	Day 0	Day 1	Day 2	Day 3	Days 8 – 10	Post-Operative Follow Up				
		Simulation	1 st Fraction	2 nd Fraction	3 rd Fraction	Surgery	24 Hours	Day of Discharge	1-3weeks	6 months	Every 6 months after surgery (Last follow up at 36 months)
Simulation		X									
SBRT			X	X	X						
Informed Consent	X										
Cancer History	X										
Demographics	X										
Inclusion/Exclusion	X										
Physical Exam	X					X	X	X	X	X	X
ECOG Performance Status (PS)	X					X					
Pre-Op Anesthesia Clearance	To be completed before surgery										
PFT	X										
Adverse Event Assessment	X (Med Hx Review)	X	X	X	X	X	X	X	X	X	X
Peri- / Post-Operative Surgical Complication Assessment						X	X	X	X	X	
Wound Healing Assessment								X	X	X	
CBC with Diff	X					X Before Surgery	X				
CMP (Serum Chemistries)	X					X Before Surgery					
BMP							X				
Urinalysis	X										
Pregnancy (URINE) Test	X										

Screening Period	Screening & Baseline	Day 0	Day 1	Day 2	Day 3	Days 8 – 10	Post-Operative Follow Up				
		Simulation	1 st Fraction	2 nd Fraction	3 rd Fraction	Surgery	24 Hours	Day of Discharge	1-3weeks	6 months	Every 6 months after surgery (Last follow up at 36 months)
Pregnancy Status Check										X	
CT Imaging of chest	X									X	X
Chest X-Ray							X		X		
Blood Collection for Translational Studies	X		X Before SBRT			X Before Surgery		X			
Tumor Tissue Collection	X (Archival)					X (Surgical Specimen)					

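### Criterion 5.1.4 requires a serum pregnancy test 48 hours before SBRT, but the protocol schedules only a urine test at screening; the contraception wording in Section 6 also needs aligning.

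*Protocol*

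**What the plan says.** **Testing.** Inclusion criterion 5.1.4 (Protocol, Section 5.1) reads: "Women of childbearing potential must have a negative serum pregnancy test 48 hours prior to initiating study intervention". Section 9.1 lists at the screening visit "Urine pregnancy test (women only"), with a window of plus or minus 7 days. The Schedule of Events (Section 9.3) has one pregnancy-test row, "Pregnancy (URINE) Test", marked only under Screening & Baseline. The only later entry is a pregnancy status check 6 months after surgery (Sections 9.1.2 and 9.3).

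**Registration.** Section 7.2 says: "Participants must meet all eligibility criteria to be eligible for registration". It accepts tests done as customary care before consent only if they fall within the time frame given in the Participant Selection section.

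**Contraception.** A general sentence in Section 6 describes adequate contraception as "hormonal or barrier method of birth control; abstinence". An itemised list later in the section accepts sexual abstinence, or one barrier method "PLUS hormonal method (oral contraceptives, implants, or injections) or an intrauterine device". The last inclusion criterion in Section 5.1 refers to the forms listed in that section.

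**The concern.** Site staff commonly build visit orders from the schedule table and the visit lists. If those omit a test that an eligibility criterion requires, the test can be missed without anyone departing from the schedule.

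Section 6 describes the intervention as possibly teratogenic and does not exclude women of childbearing potential. Section 11 handles pregnancy as a serious adverse event. A missed or wrong test would leave pregnancy status unverified before irradiation. It would also be an eligibility deviation, which Section 15.2 requires to be reported to the DSMC.

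The contraception wording matters because agreement to it is an eligibility condition, for women of childbearing potential and for men with partners of childbearing potential.

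**Working it through.** The protocol gives no figure to reproduce. The check sets every relevant passage side by side.

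**Pregnancy testing before the first fraction**

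| Place in protocol | Specimen | Timing |
|---|---|---|
| 5.1, criterion 5.1.4 | Serum | 48 hours before study intervention |
| 9.1, screening list | Urine | Screening, plus or minus 7 days |
| 9.3, Screening & Baseline column | Urine | Screening |
| 9.1.1 and 9.3, Day 0 (simulation) | None listed | – |
| 9.1.1 and 9.3, Day 1 before fraction 1 | None listed | – |

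1. *Could the serum test sit inside another blood draw?* The screening panel is itemised: it begins "Serum chemistries to include: albumin, alkaline phosphatase, ALT/SGPT, AST/SGOT, BUN, creatinine" and contains no pregnancy test. The only blood draw listed on Day 1 before the first fraction in Section 9.1.1 is "Blood collection for translational studies", and the assays described in Section 10 do not include a pregnancy test.

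2. *Could timing alone be reconciled?* The window in Section 9.1 is 7 × 24 = 168 hours either way, against 48 hours in 5.1.4. No maximum interval from screening to the first fraction is stated, so the age of the urine test at SBRT cannot be bounded. If screening did fall within 48 hours of the first fraction, the timing could agree but the specimen would still be urine. The specimen conflict therefore stands by itself.

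3. *Could the later check serve?* The 6-month status check comes after both SBRT and surgery, so it cannot support eligibility.

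4. *Count before the first fraction.* Serum tests scheduled: 0. Urine tests scheduled: 1. Tests tied to the start of SBRT: 0. No scheduled procedure documents 5.1.4.

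**Contraception (Section 6)**

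| Participant's method | General sentence | Itemised list |
|---|---|---|
| Abstinence | Met | Met |
| Listed barrier method plus hormonal method | Met | Met |
| One hormonal method alone | Met | Not met |
| One barrier method alone | Met | Not met |

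The closing reference to an intrauterine device can be read as standing alone or as an alternative to the hormonal component. Rows three and four are the same under either reading. A third sentence in Section 6 asks only for an effective form that the woman chooses, which does not resolve the difference.

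**The case against.** The strongest reply is that the schedule does not operate alone. Criterion 5.1.4 is a line on a checklist with a verification column. Section 5.2 provides sign-off lines for the coordinator, a double check and the treating physician. Section 7.2 makes every criterion a condition of registration, and Section 7.1 denies study intervention to anyone not registered. Exclusion 5.2.3 separately bars pregnant women. This stands. A reader might infer that a site following the protocol would irradiate a woman who had not had the required test, but the documents do not support that. A site following the whole protocol must obtain the serum test, even though no visit tells it to. What remains is a risk for a site that works from the schedule.

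A reader might also infer that 5.1.4 cannot be met because it refers to a time after registration. The text does not say so. Section 7.1 requires only that registration precede therapy, and Section 7.2 allows up to 24 hours for it. If the criterion means within 48 hours, a test followed by registration still leaves 48 − 24 = 24 hours before the first fraction is due. The note in Section 5.2 speaks of up to 24 business hours, which could make this tight, but both figures are upper limits.

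On contraception, the two statements are not mutually exclusive: abstinence, or a listed barrier method plus a hormonal method, satisfies both. The inclusion criterion also points to the listed forms, which favours the itemised list as the operative text. The mismatch is therefore confined to people using one method alone.

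**Conclusion.** The testing point holds. Criterion 5.1.4 conflicts with Sections 9.1 and 9.3 on specimen and on timing, and Sections 9.1.1 and 9.3 contain no later pre-treatment test that closes the gap. The consequence is a risk of an eligibility deviation and of unverified pregnancy status before SBRT, reduced but not removed by the checklist and registration step.

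The contraception point holds in a narrower form. The general sentence in Section 6 admits single methods that the itemised list does not.

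The number of people affected cannot be derived. The planned enrollment is 10, and the protocol gives no expected age or sex distribution beyond a minimum age of 18. The conclusion rests only on the protocol text as supplied and on no numerical assumption. It is a consistency and participant-safety matter, and none of the trial's estimates or descriptive summaries is affected. It should be corrected because it concerns a safeguard and costs little.

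**What to change.** Reconcile criterion 5.1.4 with Sections 9.1, 9.1.1 and 9.3 so that one specimen type and one timing appear throughout, and enter the required test in the visit list and the Schedule of Events at that time. State whether 48 hours means within or exactly that interval. In Section 6, align the general contraception sentence with the itemised list, and make the intrauterine-device wording unambiguous. Which test, interval and method apply is for the investigators and the IRB to decide.

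The cost is a wording amendment to Sections 5.1, 6, 9.1, 9.1.1 and 9.3. At most it adds one routine test to the schedule for women of childbearing potential, and the eligibility criterion already demands that test. Sample size and analysis do not change.
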